2.7.2 Overall Survival

Non-Surgery Group: overall survival (OS) is defined as the time from the date of start of treatment to the date of death due to any cause or the date of last contact (censored observation) at the date of data cutoff.

Surgery Group: OS is defined as the number of days from the first day of treatment after surgery to the date of death due to any cause or the date of last contact (censored observation) at the date of data cutoff. If the patient does not receive at least one post-surgical dose of BGJ398 (i.e., C1D1), the patient will be excluded from the overall survival analysis.

The survival time for patients without documentation of death prior to analysis data cutoff, will be censored at the last date the patient was known to be alive prior to the cutoff date. Survival time for patients with no post-baseline survival information will be censored on the date of start of treatment.

OS will be analyzed using the Kaplan-Meier method. Survival rate at 4, 6, 8, 12, 18 and 24 months and median OS will be estimated along with 95% confidence intervals.

This analysis will be done for all patients in the PPS as well as the FAS in both treatment groups pooled together.

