5.2 Inclusion criteria

Patients eligible for inclusion in this study have to meet **all** of the following criteria:

1. Patients with histologically confirmed GBM and/or other glioma subtypes at the time of diagnosis or prior relapse. Note that all subtypes of gliomas are permitted. Any question of eligibility should be discussed with Novartis.
2. At least 15-20 unstained slides and/or a tumor block from at least one prior surgery must be available for molecular testing, unless agreed otherwise between Novartis and the Investigator.
3. Written documentation of local or central laboratory determination of FGFR1-TACC1, FGFR3-TACC-3 fusion and/or activating mutation in FGFR1, FGFR2 or FGFR3 is required. Patients identified to have an activating mutation in FGFR1, 2 or 3 may be eligible pending agreement between Novartis and Investigator
4. RANO defined tumor progression by MRI (or CT for patients who cannot tolerate MRI) in comparison to a prior scan; OR, progression that does not meet RANO criteria if the disease progression is otherwise obvious in the opinion of the investigator and is discussed with Novartis OR histologically proven recurrent/progressive disease based on histology if surgery was the treatment for the most recent progression.
5. Patients must have received prior external beam radiotherapy and temozolomide.
6. Unlimited prior surgeries and chemotherapies are permitted.
7. Group specific inclusion:
 - a. Group 1: RANO defined tumor progression as per Inclusion Criteria 4. Additionally, patients who recently underwent resection for RANO defined contrast enhancing tumor progression and are post-operative without evidence of RANO tumor progression may also be eligible for group 1 assuming all inclusion/exclusion criteria are met and the most recent surgery has occurred within six weeks of the planned first treatment dose.
 - b. Group 2: RANO defined tumor progression as per Inclusion Criteria 4 and planned surgical resection. If a patient assigned to group 2 does not undergo planned surgical resection, then the patient will be allowed to continue therapy as per group 1. If a patient enrolled to group 2 needs to undergo surgical resection sooner than initially planned (and having had less than 5 days of BGJ398), then the patient will still be allowed to continue therapy post-surgically as per group 2 regardless of the number of days the patient received BGJ398 pre-surgically.
8. Patients ≥ 18 years of age.

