10.4 Primary objective

10.4.1 Variable

Preliminary tumor activity will be assessed using RANO criteria ([Appendix 3](#)).

Six month progression free-survival (PFS6) rate will be the primary efficacy variable.

For patients in group 1 (non-surgical), PFS is defined as the number of days from the first day of treatment to the date of the first documented disease progression or date of death, whichever occurs first.

For patients in group 2, who undergo surgery, PFS is defined as the number of days from the first day of treatment after surgery to the date of the first documented disease progression or date of death, whichever occurs first.

For patients in group 2, who do not undergo surgery, PFS is defined as the number of days from first day of treatment to the first documented disease progression or date of death, whichever occurs first.

Patients in group 2, who undergo surgery but do not receive at least one post-surgical dose of BGJ398 (i.e., C1D1) will be excluded from the primary efficacy analysis; their data will be listed.

[figure not shown]
The Primary Analysis will be performed on the PPS (24 patients) and the FAS summary will be provided as a supportive analysis (34 patients). The labs, safety, [REDACTED] etc, data for the patient with amplifications using the FAS will be summarized, but the efficacy focus will be on the PPS.

Patients who discontinue the study and are lost to follow-up without a known date of progression or death due to any cause on or before the cut-off date will be censored in the primary analysis at the date of their last available tumor assessment.

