10.5.2 Other secondary efficacy objectives

Objective Response Rate

A secondary objective of the study is to assess preliminary anti-tumor activity of the BGJ398 using objective response rate (ORR) as the endpoint.

Objective response rate (ORR) is defined as the proportion of patients with a best overall response of Complete Response (CR) or Partial Response (PR), as per the RANO criteria ([Appendix 3](#)).

The ORR analysis will include patients from the FAS who have measurable disease (as per RANO) at their baseline scan (as defined in [Section 7.2.1](#)). ORR will be reported with 95% confidence interval and response will be listed.

This analysis will be done for all patients in the PPS as well as the FAS in both treatment groups pooled together.

Overall Survival

For patients in group 1, overall survival (OS) is defined as the time from the date of start of treatment to the date of death due to any cause or the date of last contact (censored observation) at the date of data cutoff.

For patients in group 2, who undergo surgery, OS is defined as the number of days from the first day of treatment after surgery to the date of death due to any cause or the date of last contact (censored observation) at the date of data cutoff.

For patients in group 2, who do not undergo surgery, OS is defined as the number of days from first day of treatment to the date of death due to any cause or the date of last contact (censored observation) at the date of data cutoff.

Patients in group 2, who undergo surgery but do not receive at least one post-surgical dose of BGJ398 (i.e., C1D1) will be excluded from the overall survival analysis; their data will be listed.

The survival time for patients without documentation of death prior to analysis data cutoff, will be censored at the last date the patient was known to be alive prior to the cutoff date. Survival

time for patients with no post-baseline survival information will be censored on the date of start of treatment.

OS will be analyzed using the Kaplan-Meier method. Survival rate at 4, 6, 8, 12, 18 and 24 months and median OS will be estimated along with 95% confidence intervals. All patients in the FAS except patients in group 2, who undergo surgery but do not receive at least one post-surgical dose of BGJ398 will be included in this analysis.

This analysis will be done for all patients in the PPS as well as the FAS in both treatment groups pooled together.

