2.5.1 Primary endpoint

PFS rate at 6 months (PFS6) as defined by RANO criteria assessed by the investigator will be the primary endpoint.

[figure not shown]
Non Surgery Group: PFS is defined as the number of days from the first day of treatment to the date of the first documented disease progression or date of death, whichever occurs first.

Surgery Group: PFS is defined as the number of days from the first day of treatment after surgery to the date of the first documented disease progression or date of death, whichever occurs first.

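### SAP 2.7.2, read literally, removes unoperated Surgery Group patients from overall survival, and the SAP leaves their PFS start date and baseline scan undefined, although the protocol defines all three

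*SAP*

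**What the plan says.** The protocol foresees a group 2 patient whose operation does not take place. Under inclusion criterion 7b (section 5.2), a patient assigned to group 2 who "does not undergo planned surgical resection, then the patient will be allowed to continue therapy as per group 1" remains on study drug.

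The protocol's statistical section gives that patient a separate rule for each endpoint:

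- Protocol 10.4.1, PFS: "For patients in group 2, who do not undergo surgery, PFS is defined as the number of days from first day of treatment".
- Protocol 10.5.2, OS: "For patients in group 2, who do not undergo surgery, OS is defined as the number of days from first day of treatment".
- Protocol 10.5.2, OS exclusion: "Patients in group 2, who undergo surgery but do not receive at least one post-surgical dose of BGJ398 (i.e., C1D1) will be excluded". Protocol 10.4.1 makes the same exclusion from the primary efficacy analysis.

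The SAP has one rule per endpoint for the whole Surgery Group:

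- SAP 2.5.1: "Surgery Group: PFS is defined as the number of days from the first day of treatment after surgery".
- SAP 2.7.2: "Surgery Group: OS is defined as the number of days from the first day of treatment after surgery", followed by "If the patient does not receive at least one post-surgical dose of BGJ398 (i.e., C1D1), the patient will be excluded from the overall survival analysis".

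For the baseline scan, protocol 7.2.1 treats unoperated group 2 patients like group 1. SAP 2.1.1 ties the Surgery Group's efficacy baseline to the date of surgery and has no line for patients without surgery. SAP section 4 lists one change from the protocol: the interim analysis was not performed.

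**The concern.** The protocol has three cases: group 1, group 2 operated, and group 2 not operated. The SAP has two. Its OS exclusion also loses the condition that the patient had surgery. A patient who is never operated on cannot have a dose after surgery, so the literal SAP rule takes that patient out of OS in both the FAS and the PPS runs.

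These patients are treated and followed, and their continuation is allowed by the protocol. Their removal depends on something that happens after the first dose. If the reason for cancelling surgery is related to prognosis, removing them biases the survival curve.

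For PFS the problem is different. The start date in SAP 2.5.1 does not exist for such a patient, and the SAP does not say what to do. The missing baseline rule adds to this, because PPS membership (SAP 2.2) requires an adequate baseline tumor assessment and the PPS carries the primary analysis.

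**Working it through.** **1. Side-by-side reading for a group 2 patient who is dosed, not operated on, and continues on drug**

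| Item | Protocol | SAP |
|---|---|---|
| OS start | First treatment day (10.5.2) | First treatment day after surgery, which does not exist (2.7.2) |
| In OS analysis? | Yes; the exclusion needs surgery to have happened (10.5.2) | No, read literally (2.7.2) |
| PFS start | First treatment day (10.4.1) | First treatment day after surgery, which does not exist (2.5.1) |
| In PFS analysis? | Yes (10.4.1) | Not stated; 2.5.1 has no exclusion |
| Baseline scan | As for group 1 (7.2.1) | Not stated (2.1.1) |
| Declared as a change? | – | No (section 4) |

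No SAP sentence moves such a patient to the Non Surgery Group. Table 2-3 (SAP 2.2) lists no exclusion for them.

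**2. How many patients**

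Protocol 4.1 expects about 2:1 for group 1 to group 2 among the 34 enrolled, so group 2 is 34 / 3 = 11.3, about 11 patients. The documents give no rate of cancelled surgery. Assuming 0 to 30%, the number affected is 0 to 0.30 × 11 = 3.3, that is 0 to 3 patients. One patient is 1/34 = 2.9% of the planned enrolment and 1/24 = 4.2% of the planned PPS.

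**3. Check of the model against the plan's own figures**

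The model is Weibull, S(6) = exp(−λ·6^ν), with log λ ~ N(0, 2.236) and ν ~ Exp(1), time in months, and the posterior taken on a grid. Simulations used 1000 trials per scenario, exponential PFS and one patient per month.

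- Prior P(PFS6 < 16%): 0.649 (stated 65%). Prior P(PFS6 > 40%): 0.257 (stated 25%).
- N = 34, interim at 17 (size taken from the protocol summary), true PFS6 50%: success 0.907 to 0.919 (SAP Table 3-1: 0.917).
- N = 24, interim at 10, true PFS6 50%: success 0.872 to 0.877 (protocol Table 10-2: 0.861).

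The model agrees with the stated figures to within 2 points.

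**4. PFS6 if the gaps lead to omission: worst case**

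Assumptions: 24 patients, of whom k are unoperated and progress at month 2. The other 24 − k follow exponential quantiles with PFS6 of 40%. Results are averaged over 40 entry orders.

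| k | P(PFS6 ≥ 40%), kept | Left out | Difference |
|---|---|---|---|
| 1 | 0.43 | 0.49 | 0.06 |
| 2 | 0.37 | 0.48 | 0.11 |

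Repeat runs with other entry orders moved the levels by a few hundredths (kept 0.37 to 0.44, left out 0.46 to 0.53). The differences stayed at 0.05 to 0.06 for one patient and 0.11 to 0.12 for two. The success rule requires this probability to exceed 0.50.

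**5. PFS6 if the omitted patients are like the rest**

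Simulated success at true PFS6 50% without an interim is 0.91 for both N = 34 and N = 31. It is 0.89 for N = 24 and 0.87 for N = 21 (simulation error about 0.01). Only a little precision is lost.

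**The case against.** A reader might infer that the SAP also excludes these patients from the primary PFS6 analysis. It does not say so. SAP 2.5.1 contains no exclusion, and SAP 2.1.1 names the start of study treatment as the reference date for all assessments, including efficacy. That sentence defines study day and not the PFS clock, so it does not close the gap. It does offer a natural default, and it is the protocol's own origin for these patients.

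A reader might also infer that cancelled surgery means deterioration, so that early failures are being removed. The documents give no reason for cancellation, and the month-2 progression above is purely an assumption.

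A lenient reading of SAP 2.7.2 is possible. The clause glosses the post-surgical dose as cycle 1 day 1, and an unoperated patient who continues like group 1 may have a cycle 1 day 1 record. The SAP's FAS definition omits the protocol's classification by planned treatment (10.1.1), so analysing such patients with the Non Surgery Group is not barred. Protocol Appendix 3 uses the same two-case shorthand, which suggests abbreviation and not a deliberate change.

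Finally, OS is a descriptive Kaplan-Meier endpoint without a success rule, and SAP 2.2 allows for an empty surgery group.

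These points limit the size of the problem and suggest a drafting loss. They do not remove it: the SAP adopts none of the lenient readings, and its literal OS rule contradicts protocol 10.5.2.

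**Conclusion.** The inconsistency is real and undeclared. For OS, the SAP as written excludes treated patients whom the protocol includes. For PFS and the baseline scan, it leaves undefined what the protocol defines. It does not go so far as to remove them from the primary analysis.

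The direct effect is on OS: 2.9% of planned enrolment per unoperated patient, or 0 to 3 patients if 0 to 30% of about 11 are not operated on (an assumed range). The direction of any OS bias cannot be stated from the documents.

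An effect on PFS6 arises only if the missing start date or baseline leads to patients being left out. The rise in P(PFS6 ≥ 40%) of about 0.06 for one patient and 0.11 for two is a worst case. It is close enough to the 0.50 threshold to matter in a borderline result. If these patients have the same PFS as the others, the loss is one of precision only. If every Surgery Group patient is operated on, or the group is empty, the effect is zero. The point should be corrected, but it does not undermine the design.

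**What to change.** - **SAP 2.5.1 and 2.7.2:** add the third case. For Surgery Group patients who are not operated on, PFS and OS run from the first day of treatment.
- **SAP 2.5.1 and 2.7.2:** limit the exclusion to patients who have surgery and then receive no post-surgical dose. State it for PFS as well as OS, because SAP 2.5.1 currently omits the PFS exclusion in protocol 10.4.1.
- **SAP 2.1.1:** add that unoperated Surgery Group patients take the baseline scan rule of the Non Surgery Group. Refer to protocol 7.2.1 for that rule, because the SAP's own sentence places the Non Surgery scan after the start of treatment, whereas protocol 7.1 requires baseline imaging before the first dose.
- **If the narrower analysis is intended:** declare and justify it in SAP section 4.

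The cost is a few sentences and one extra branch in the derivation of start dates and baseline. No stated design figure changes.

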2.8 Safety analyses

A secondary objective of the study is to characterize the safety and tolerability of BGJ398.

The assessment of safety is based on the frequency and severity of AEs and SAEs, changes in hematology and chemistry values, specifically those associated with calcium/phosphate homeostasis and renal function, and on the number of laboratory values that fall outside of pre-determined ranges (CTCAE v 4.03 grading limits or normal ranges as appropriate). Other safety (e.g., ECGs, vital signs and special tests, e.g. pregnancy test) analyses will be considered as appropriate.

All safety analyses will be based on the safety set.

The safety summary tables will include only on-treatment assessments. All safety assessments will be listed, and those collected later than 30 days after study treatment discontinuation will be flagged.

2.8.1 Adverse events (AEs)

AE summaries

AEs will be coded using MedDRA terminology, the latest version which will be available at the time of analysis.

AE summaries will include all AEs occurring during on treatment period. All AEs collected in the AE (e)CRF page will be listed along with the information collected on those AEs e.g. AE

relationship to study drug, AE outcome etc. AEs with start date outside of on-treatment period will be flagged in the listings.

AEs will be summarized by number and percentage of subjects having at least one AE, having at least one AE in each primary system organ class (SOC) and for each preferred term (PT) using MedDRA coding. A subject with multiple occurrences of an AE will be counted only once in the respective AE category. A subject with multiple CTCAE grades for the same preferred term will be summarized under the maximum CTCAE grade recorded for the event. AE with missing CTCAE grade will be included in the 'All grades' column of the summary tables.

In AE summaries, the primary system organ class will be presented alphabetically and the preferred terms will be sorted within primary SOC in descending frequency. The sort order for the preferred term will be based on their frequency.

The following adverse event summaries will be produced:

- Overview of adverse events and deaths (number and % of subjects who died, with any AE, any SAE, any dose reductions/interruptions, AE leading to discontinuation);
- AEs by SOC and PT, summarized by relationship (all AEs and AEs related to study treatment);
- Seriousness (SAEs and non-SAEs);
- Leading to treatment discontinuation;

The following listings will be produced:

- All adverse events (safety set)
- Adverse events among subjects who were not treated (all screened subjects)

Deaths

- Summaries for on-treatment and all deaths (including post-treatment death) will be produced by system organ class and preferred term.
- All deaths will be listed for the safety set, post treatment deaths will be flagged. A separate listing of deaths prior to starting treatment will be provided for all screened subjects.

EudraCT and clinicaltrials.gov requirements for AEs and Deaths summaries For the legal requirements of clinicaltrials.gov and EudraCT, two required tables on treatment-emergent adverse events which are not serious adverse events with an incidence greater than 5% and on treatment emergent SAEs and SAEs suspected to be related to study treatment will be provided by SOC and PT on the safety set population.

If for a same patient, several consecutive AEs (irrespective of study treatment causality, seriousness and severity) occurred with the same SOC and PT:

- a single occurrence will be counted if there is ≤ 1 day gap between the end date of the preceding AE and the start date of the consecutive AE
- more than one occurrence will be counted if there is > 1 day gap between the end date of the preceding AE and the start date of the consecutive AE

For occurrence, the presence of at least one SAE / SAE suspected to be related to study treatment / non SAE has to be checked in a block e.g., among AE's in a ≤ 1 day gap block, if at least one SAE is occurring, then one occurrence is calculated for that SAE.

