1.2.1.2 Clinical experience

1.2.1.2.1 Clinical safety

As of November 6, 2014, 226 patients have received BGJ398 on one of the eight clinical trials. In addition to this phase II trial, BGJ398 is being evaluated in three phase I trials, one other monotherapy phase II study, two healthy volunteer studies and an individual patient protocol

(protocol to patient trial) that provides BGJ398 treatment to patients with tumors with FGFR genetic alterations who are not covered by available trials or are unable to travel to study centers. The dose escalation portion of the first in human phase I study (CBGJ398X2101) has been completed and the MTD has been identified as 125 mg once daily (q.d.), administered continuously. BGJ398 was evaluated at 9 different dose levels, ranging from 5 mg per day to 150 mg per day. The adverse events suspected to be related to BGJ398 that occurred in more than 20% or more patients who received BGJ398 were hyperphosphatemia (71.3%), decreased appetite (26.6%), fatigue (25.5%), stomatitis (24.5%), and alopecia (21.3%). Twenty-seven percent of patients (26/94) experienced at least one grade 3 or 4 event. Overall, most adverse events reported have been mild to moderate in severity and unrelated to BGJ398. Please refer to Investigator Brochure for more information.

Four dose limiting toxicities (DLTs) were reported during the dose escalation portion and occurred at the 100 mg (n=1; grade 3 AST/ALT elevation), 125 mg (n=1; hyperphosphataemia for > 14 days), and 150 mg (n=2; grade 1 corneal toxicity and grade 3 AST/ALT elevation) dose levels.

Enrollment is continuing in the dose expansion phase of the study at the 125 mg dose level in three out of four arms. One arm, which enrolled patients with any solid tumor type with FGFR genetic pathway alterations on a continuous schedule, has been closed due to completing enrollment. Of the three open arms, one arm is enrolling patients with FGFR1-amplified squamous non-small cell lung cancer, with dosing on a continuous 28 day cycle. A second arm is enrolling patients with advanced solid malignancies with any FGFR alteration and a third arm is enrolling patients with advanced or metastatic urothelial cell carcinoma with FGFR mutation or gene fusion. Patients enrolled to these latter two arms receive BGJ398 at 125 mg q.d. on a 3 weeks on/1 week off drug schedule, repeated in 28 day cycles.

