The treatment emergent adverse events that occurred in 20% or more patients that were reported as of October 1, 2014 were increases in blood phosphorus [which include AE term of hyperphosphatemia] (74%), constipation (40.8%), decreased appetite (40.8%), diarrhea (36.7%), stomatitis (36.7%), nausea (32.5%), fatigue (31.7%), alopecia (25.8%), asthenia (20.0%), blood creatinine increased (20.0%), and dry mouth (20.0%). The majority of the adverse events were Grade 1 and 2 and were reversible upon discontinuation of study drug. Additional information about the nature of these AEs and the dose levels at which they occurred can be found in the most recent version of the BGJ398 Investigator Brochure. Hyperphosphatemia has been seen in the majority of patients treated at doses of 100 mg q.d. and higher. Phosphate elevations are a biomarker of on-target FGFR pathway inhibition which mediates renal tubular phosphate secretion and reabsorption. Inhibition of this pathway leads to inability to secrete phosphate and secondary elevations in FGF23. The hyperphosphatemia has been managed in Phase I study by dietary phosphate restrictions, phosphate lowering therapy, drug interruptions, and dose reductions, which led to the introduction of the alternate 3 weeks on/1 week off drug schedule. Preliminary safety data with this schedule suggests improved tolerability and compliance with drug administration (e.g. fewer dose interruptions during cycle 1), though dose reductions in later cycles of therapy are not uncommon. As of March 15, 2014 data cut off, 17 out of 25 patients (68%) who received BGJ398 on the 3 week on/1 week of schedule experienced elevated phosphorus and only 4 patients (16%) required cycle 1 interruptions or reductions. In contrast, 41 out of 47 patients (87%) on the continuous dosing cycle experienced serum phosphorus

elevations. Twenty patients (43%) required cycle 1 dose interruptions and 13 patients (28%) required dose reductions during cycle 1. Please refer to the BGJ398 Investigator Brochure for additional information.

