8.1.2 Laboratory test abnormalities

8.1.2.1 Definitions and reporting

Laboratory abnormalities that constitute an Adverse event in their own right (are considered clinically significant, induce clinical signs or symptoms, require concomitant therapy or require changes in study treatment), should be recorded on the Adverse Events CRF. Here as well, whenever possible, a diagnosis, rather than a symptom should be provided (e.g., anemia instead of low hemoglobin). Laboratory abnormalities that meet the criteria for Adverse Events should be followed until they have returned to normal or an adequate explanation of the abnormality is found. When an abnormal laboratory or test result corresponds to a sign/symptom of an already reported adverse event, it is not necessary to separately record the lab/test result as an additional event.

Laboratory abnormalities, that do not meet the definition of an adverse event, should not be reported as adverse events. A Grade 3 or 4 event (severe) as per CTCAE does not automatically indicate a SAE unless it meets the definition of serious as defined below and/or as per investigator's discretion. A dose hold or medication for the lab abnormality may be required by

the protocol in which case the lab abnormality would still, by definition, be an adverse event and must be reported as such.

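### SAP 2.8.1 plans no grouped adverse-event term for raised phosphorus, so if sites use more than one term, no single preferred-term row gives the number of patients affected or their maximum grade

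*SAP*

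**What the plan says.** **Adverse-event tables.** SAP 2.8.1 counts patients with any event and patients "having at least one AE in each primary system organ class (SOC) and for each preferred term (PT) using MedDRA coding". The planned summaries include "AEs by SOC and PT, summarized by relationship (all AEs and AEs related to study treatment"), together with summaries by seriousness and of events leading to treatment discontinuation. A patient with several grades of one preferred term is shown at the highest of them. The two registry tables "will be provided by SOC and PT on the safety set population". The visible SAP text defines no grouped term and no event of special interest, and neither does Protocol 10.5.3.2.

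**Laboratory tables.** SAP 2.8 bases safety partly on laboratory changes, "specifically those associated with calcium/phosphate homeostasis and renal function". In SAP 2.8.2, however, Table 2-4 names phosphate only in the low direction (hypophosphatemia), and Table 2-5 does not list phosphorus.

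**Program figures.** Protocol 1.2.1.2.1 reports the treatment-emergent rate as "increases in blood phosphorus [which include AE term of hyperphosphatemia] (74"%). The same section gives, for drug-related events, "hyperphosphatemia (71.3%), decreased appetite (26.6%), fatigue (25.5%), stomatitis (24.5%), and alopecia (21.3"%). It also reports elevated phosphorus in 17 of 25 patients (68%) on the 3-weeks-on, 1-week-off schedule that this trial uses. Protocol 2.3 names hyperphosphatemia as the main toxicity behind dose interruptions.

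**Reporting rule for sites.** Protocol 8.1.2.1 says that "whenever possible, a diagnosis, rather than a symptom should be provided (e.g., anemia instead of low hemoglobin"). Protocol 8.1.1 says much the same. Section 8.1.2.1 adds that a laboratory result belonging to an event already reported need not be recorded again.

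**The concern.** The bracket in the protocol's 74% entry makes sense only if more than one reported term captures the same harm. The program has therefore already had to combine terms to count the patients affected, and the SAP does not carry that counting rule into this trial.

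The type, frequency and severity of adverse events is a secondary endpoint (SAP Table 1-1). If some patients are recorded under one term and some under another, a reader of the preferred-term tables sees two rows. Neither row is the number of patients with raised phosphorus. Severity is affected in the same way, because the maximum grade is taken within each preferred term. The worst phosphorus event of a patient with both terms is then not summarized across them.

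The named laboratory tables are not sure to supply the missing number, since they list only low phosphate. Protocol 10.5.3.3 and the general rules in SAP 2.8.2 and 5.3 could be read as covering high values, but no named row does so. The adverse-event tables therefore carry more weight for this harm than they otherwise would.

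**Working it through.** **1. What the program figures are.**
- The 68% reproduces directly: 17/25 = 0.68.
- The 74% has no stated count or denominator. A search over denominators from 20 to 226 finds only 120 compatible with every percentage in that sentence, giving 89/120 = 74.2%. That denominator is inferred, not stated.
- The 71.3% is consistent with 67/94 = 71.3%. The denominator 94 stands in the following sentence: "Twenty-seven percent of patients (26/94) experienced at least one grade 3 or 4 event".
- The 74% covers all treatment-emergent events with terms combined. The 71.3% covers drug-related events with no grouping stated, and the denominators appear to differ. The gap of 74 − 71.3 = 2.7 points therefore does not measure any effect of splitting.

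**2. Bound on a single row.** Let a and b be the numbers of patients with each of two terms, and u the number with either. Then max(a, b) ≤ u ≤ a + b. It follows that:
- the larger row lies between u/2 and u, so it can equal u or fall below it, but cannot exceed it;
- the sum a + b overcounts by the number of patients with both terms, which the tables do not show.

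**3. Illustration for this trial.** Inputs: 34 planned patients (Protocol 4.1 and 10.4.1), used as a proxy for the safety set, and the 68% for this dosing schedule.
- Patients affected: 34 × 0.68 = 23.1, about 23.
- Largest possible row (no split): 23/34 = 67.6%.
- Smallest possible larger row (even split, no overlap): 23/2 = 11.5, so 12 whole patients, and 12/34 = 35.3%.

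If a share s of affected patients is coded only to the second term and all others carry the first, the first row shows 68% × (1 − s):

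| s (assumed) | First row |
|---|---|
| 0 | 68.0% |
| 0.10 | 61.2% |
| 0.25 | 51.0% |
| 0.50 | 34.0% |

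The last line differs from 12/34 only because whole patients were used above. The documents give no value for s.

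**4. Does the reporting rule fix s at zero?** It pushes in that direction. It asks for a diagnosis where possible and does not require a second entry for a result already covered. It still leaves room for an event to be entered as a laboratory finding. The program's own list in Protocol 1.2.1.2.1 contains such an entry, blood creatinine increased (20.0%). So s may be zero, but the documents do not guarantee it.

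**The case against.** The strongest reply is that no loss has been shown. A reader might infer that hyperphosphatemia will be split and its incidence understated. The documents do not support that: it depends on how sites report and how terms are coded, and the diagnosis-first and no-duplicate rules may leave a single term in use. This stands, and the point is conditional for that reason.

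Other tempting readings also go too far:

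- **That this trial would look falsely better than 74%.** Neither document plans that comparison, and 74% appears only as background. The protocol gives 68% on this schedule against 87% (41/47) on continuous dosing, and phosphate binders are used prophylactically (Protocol 2.3). A rate below 74% would be unsurprising whatever the coding.
- **That the terms fall under different system organ classes, so no class row recovers the count.** That depends on the coding dictionary, not on these documents, and is not relied on here.
- **That the SAP counts only by single preferred term.** Any-event and class counts are also planned, as are full event listings and dose reductions and interruptions with reasons. Both term rows would be printed, and a reader could remove duplicates from the listings. That would be work after the fact, though, and not a planned incidence.

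Finally, the SAP leaves table detail to separate shells that are not among the documents, so a grouped row may exist there. However, the SAP introduction says that the SAP itself describes all planned analyses for the report, so the rule belongs in its text.

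**Conclusion.** The point holds in conditional form. The SAP has no grouped term for the main known toxicity, while the protocol reports that toxicity with terms combined. If more than one term is used, no single preferred-term row is sure to give the number of patients affected or their maximum grade. The direction is certain: equal or lower, never higher.

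The size is unknown and may be zero. The range of 12/34 to 23/34 is an illustration. It assumes 68% incidence, 34 patients in the safety set and exactly two terms.

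This is an inexpensive improvement to the reporting plan, not a demonstrated error. It affects neither the primary analysis nor any clinical rule.

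**What to change.** In SAP 2.8.1, prespecify one grouped row for increased blood phosphorus, covering the hyperphosphatemia and blood-phosphorus-increased terms. Count each patient once, at the maximum grade across those terms. Show the row in the all-cause, related, serious and leading-to-discontinuation tables. Freeze the list of preferred terms before database lock. Keep the class and preferred-term tables as planned, and use the grouped row for any comparison with the program's grouped figure.

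The cost is a sentence and a short term list in the SAP, plus one extra row set per table, from data already collected. The reported incidence may be less favorable. If only one term turns out to be used, the grouped row equals the preferred-term row and nothing is lost.
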